Introduction: Glycemic control in acutely ill stroke patients with hyperglycemia is vital. Although insulin is the choice of anti-diabetic agent during acute stage, it is not clear which insulin regimen is better in terms of glycemic control and prevention of hypoglycemia in hospitalized acute stroke patients who are usually on small frequent nasogastric tube feeding. The present study aims to evaluate the efficacy and safety of human insulin (regular insulin and neutral protamine hagedorn, NPH insulin) to analog insulin (basal insulin glargine and rapid acting insulin aspart) in hospitalized acute stroke patients with hyperglycemia.

Justification: Analog insulins are developed by minor alteration of the amino acid chain which alters their pharmacokinetics and make them more physiological. However, these insulins are costly and are not widely available. Conventional human insulins are more commonly used in our country. Comparison of these two regimen is necessary in our own setting to optimize optimal glycemic management of hospitalized acute stroke patients.

Methodology: In this single-center, open-label, randomized trial, 100 patients with acute stroke and hyperglycemia (capillary blood glucose ≥ 10 mmol/L on 2 or more occasions) or history of type 2 DM admitted in the in-patient Department of Neurology, National Institute of Neurosciences (NINS) & Hospital will be randomly assigned to receive human insulin or modern insulin therapy in 1:1 ratio. The study will be carried out from February to June 2021. Blood glucose (BG) will be monitored by standardized glucometer thrice a day and insulin dose will be adjusted daily. The primary outcome of the study will be the differences in glycemic control between groups, as measured by mean daily BG concentration during the hospital stay. Secondary outcomes include differences between treatment groups in any of the following measures: number of hypoglycemic events (BG < 3.9 mmol/L), total daily dose of insulin, length of hospital stay, hospital complications and mortality.

Expected outcome/ result: The result will clearly show the efficacy and safety of newer insulins in comparison to conventional human insulin.

Recommendation: The study may help generating recommendations about insulin use in hospitalized acute stroke patients.

Section-C

INTRODUCTION:

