It is well known that good clinical outcome in hospitalized patients with hyperglycemia cannot be expected unless target blood glucose is promptly achieved and maintained (1-3). This is also true for acute stroke patients. Hyperglycemia may affect the outcome of both ischemic and hemorrhagic stroke (4-6). Pro-oxidative and proinflammatory state imposed by hyperglycemia can cause direct neuronal toxicity. An increase of cerebral edema may be caused by hyperglycemia-mediated increase in matrix metalloproteinase-9 causing neuronal damage. Moreover, hyperglycemia may be responsible for a procoagulant state that can further compromise blood supply to the penumbral areas in acute ischemic stroke (7).

Management of hyperglycemia in acute stroke patients is particularly challenging because many of the patients cannot take their usual food and need feeding by nasogastric (NG) tube. Common practice is to feed 200 ml of liquid food (soup or milk) 2 hourly starting at morning and continue up to night (10 feeds/day). As such, insulin regimen used to control hyperglycemia in patients taking three major meals may not be appropriate in this setting. Moreover, many acute stroke patients receive corticosteroid therapy, which further deteriorates glycemic status. Dislodgement of NG tube may result in interruption of interruption of feeding, predisposing to hypoglycemia. All these challenges need to be kept in mind while choosing appropriate insulin regimen.

Hyperglycemia in hospitalized patients is defined as blood glucose levels >7.8 mmol/L. Insulin therapy should be initiated for treatment of persistent hyperglycemia starting at a threshold ≥ 10.0 mmol/L. Once insulin therapy is started, a target glucose range of 7.8–10.0 mmol/L is recommended for the majority of critically and non-critically ill patients (8). More stringent goals, such as <7.8 mmol/L may be appropriate for selected patients, as long as this can be achieved without significant hypoglycemia.

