- To evaluate the efficacy and safety of human insulin (regular insulin and intermediate acting NPH insulin)
- To assess the efficacy and safety of insulin analog (basal insulin glargine and rapid acting insulin aspart)
- To compare the efficacy and safety of two insulin regimen
- To evaluate the socio-demographic and clinical characteristics of the patients included in two treatment arms

METHODOLOGY:

Type of study: Single-center, open-label, randomized trial

Place of Study: Department of Neurology, National Institute of Neurosciences & Hospital, Dhaka.

Study Period: February to June, 2021

Study population: Patients admitted in the Department of Neurology with acute stroke and hyperglycemia

Sample Size:

Sample size was calculated according to following formula for non-inferiority trial (17):

$$N = 2 \times \left(\frac{Z_{1-\alpha} + Z_{1-\beta}}{\delta_0} \right)^2 \times S^2$$

Here, N= sample size per group

$$\alpha = 0.05$$

$$\beta = 0.20$$

δ_0 = a clinically acceptable margin (assumed as 3 mmol/L of blood glucose)

S² = Pooled standard deviation of both comparison group = 8

So,

$$N_{\text{non-inferiority}} = 2 \times \left(\frac{1.645 + 0.845}{3} \right)^2 \times 6^2 = 50$$

As a result, 50 patients will be randomly assigned to two treatment groups (50 human insulin regimen, 50 analog insulin regimen).

Inclusion criteria

- Patients admitted to adult neurology ward with acute stroke with
- Patients having hyperglycemia (capillary blood glucose ≥ 10 mmol/L in 2 or more occasions or having history of treatment for DM)
- Patients with age of 18-80 years of both sexes
- Patients or their attendants giving consent to take part in the study

Exclusion Criteria

- Patients with hyperglycemic emergencies (hyperglycemic hyperosmolar state or diabetic ketoacidosis)
- Pregnant patients
- Those not giving consent to participate in the study

Study Procedure

Patients will be randomly assigned to receive either a human insulin regimen (starting with regular insulin three times a day with NPH insulin twice a day) or analog insulin regimen (basal insulin glargine once daily and insulin aspart three times a day) following a computer-generated randomization table. All oral antidiabetic drugs will be discontinued on admission.

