For a patient who is known to have diabetes but were not getting insulin previously (or previous insulin dosage is not known), insulin therapy will be started at a total daily dose of 0.3-0.4 units/kg/day for an admission BG between 10-15 mmol/L or 0.5-0.6 units/kg/day for a BG >15 mmol/L. In previously insulin treated patients, ongoing total daily dose of insulin will be started. If there is history of poor glycemic control with ongoing insulin dose, then 10-20% increase of daily dose of insulin will be considered.

For a patient who is not known to have diabetes, insulin therapy will be started if admission BG is >10 mmol/L in two or more occasions. A total daily dose of 0.3-0.4 units/kg/day will be started if admission BG is 10-15 mmol/L and 0.5-0.6 units/kg/day for a BG >15 mmol/L.

Patients treated with human insulin regimen will receive 50% of total daily dose as NPH insulin at around 6 am and 6 pm, while the rest 50% regular human insulin three times a day in 3 equally divided doses at around 6 am, 12 pm and 6 pm.

Patients treated with modern insulin regimen will receive 50% of total daily dose as basal insulin glargine at the same time of day and 50% as insulin aspart given in 3 equally divided doses at 6 am, 12 pm and 6 pm.

In both groups, insulin dosage will be adjusted daily to a target fasting and premeal BG 7.8-10.0 mmol/L in the absence of hypoglycemia. Insulin dosage will be adjusted daily according to BG values. If the fasting and/or premeal BG is 10-15 mmol/L in the absence of hypoglycemia, the total daily dose will be increased by 10% every day. If the fasting and/or premeal BG is >15 mmol/L, the insulin daily dose will be increased by 20% every day. If a patient develops hypoglycemia (BG <3.9 mmol/L), the insulin daily dose will be decreased by 20%. Supplemental regular insulin will be given in addition to scheduled mealtime insulin for BG >10 mmol/L using a supplemental insulin protocol.

BG will be measured before each bolus insulin injection (at 6 am, 12 pm and 6 pm). Glycated hemoglobin (HbA1c) will be measured after hospital admission if not done within last three months.

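### A history of diabetes treatment alone counts as hyperglycemia at entry, which conflicts with the stated population and leaves some eligible patients without a starting-dose rule

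*Combined protocol and SAP*

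**What the plan says.** The study population under Methodology is "Patients admitted in the Department of Neurology with acute stroke and hyperglycemia", and the general and specific objectives carry the same restriction. The Introduction sets two thresholds: "Hyperglycemia in hospitalized patients is defined as blood glucose levels >7.8 mmol/L", and "Insulin therapy should be initiated for treatment of persistent hyperglycemia starting at a threshold ≥ 10.0 mmol/L".

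The Inclusion criteria define the glucose condition as "Patients having hyperglycemia (capillary blood glucose ≥ 10 mmol/L in 2 or more occasions or having history of treatment for DM". The summary and the abstract for the ethics committee put it differently: "hyperglycemia (capillary blood glucose ≥ 10 mmol/L on 2 or more occasions) or history of type 2 DM admitted". No exclusion criterion concerns low or on-target glucose.

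Study Procedure stops all oral antidiabetic drugs on admission and randomises every entrant to one of two insulin regimens. Its starting rules are:

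- Known diabetes, no previous insulin or dose unknown: "insulin therapy will be started at a total daily dose of 0.3-0.4 units/kg/day for an admission BG between 10-15 mmol/L", and a higher band above 15 mmol/L.
- Previously insulin-treated: the ongoing total daily dose, with no glucose condition (an increase is considered if control was poor).
- Not known to have diabetes: insulin starts if admission glucose is above 10 mmol/L on at least two occasions, with the same two dose bands.

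The section on protocol deviation and violation treats unmet inclusion or exclusion criteria as a violation and discards that participant's data.

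**The concern.** Three parts of the protocol describe different patients. The objectives concern patients with hyperglycemia. The entry rule also takes treated diabetics at any glucose level, including those already inside the 7.8-10.0 mmol/L target. The starting rules for diabetics not on insulin assume at least 10 mmol/L.

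Three things are at stake:

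- **Treatment as delivered.** Where no rule applies, the starting dose is left to investigators who know the allocation, since the trial is open-label. Hypoglycemia is the primary safety outcome.
- **Who is analysed.** Two history definitions and two glucose thresholds, combined with a rule that discards data for unmet criteria, leave room to decide after randomisation who counts.
- **The comparison itself.** If the regimens differ less in patients who enter with lower glucose, a real difference in mean daily glucose becomes harder to detect.

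**Working it through.** **1. Does history alone suffice?** In the Inclusion criteria, treatment history stands inside the parenthesis that defines hyperglycemia, as an alternative to two readings of at least 10 mmol/L. In the summary the parenthesis closes first, and history is an alternative to hyperglycemia itself. On either wording, history alone is enough.

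**2. Which of these entrants have a starting rule at admission glucose below 10 mmol/L?**

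| Patient | Eligible under Inclusion criteria | Starting rule |
|---|---|---|
| Treated diabetes, previous insulin, dose known | Yes | Yes: ongoing dose |
| Treated diabetes, previous insulin, dose unknown | Yes | None below 10 |
| Treated diabetes, no previous insulin | Yes | None below 10 |

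The gap covers the last two rows only.

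**3. Do the criteria agree across sections?**

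- Untreated type 2 diabetes, glucose below 10: eligible by the summary and abstract, not by the Inclusion criteria.
- Treated diabetes other than type 2, glucose below 10: eligible by the Inclusion criteria, not by the summary and abstract.
- No known diabetes, two readings of exactly 10.0: eligible (at least 10), but the condition for starting insulin (above 10) is not met.

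**4. The plan's own sample size.** Inputs from Sample Size: margin 3 mmol/L, one-sided alpha 0.05, beta 0.20, SD 6 as used in the arithmetic line.

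N = 2 × ((1.645 + 0.845)/3)² × 6² = 49.6, so 50 per group. The stated figure reproduces, and the eligibility point does not change it. (The same section declares the value 8, not 6. That is a separate discrepancy, so both are carried below.)

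**5. Possible loss of power.** Statistical analysis plans two-tailed tests at 0.05. Assumptions not in the documents: a share f enters on history alone with glucose below 10; the difference between regimens is 3 mmol/L in the other patients and zero in these; the SD is unchanged.

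- Average difference: d = 3 × (1 − f).
- Standard error with 50 per arm: 6 × √(2/50) = 1.20 for SD 6, and 8 × √(2/50) = 1.60 for SD 8.
- Power ≈ Φ(d/SE − 1.96).
- Example, f = 20%, SD 6: d = 2.4, 2.4/1.20 − 1.96 = 0.04, power 51.6%.

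| f | d (mmol/L) | Power, SD 6 | Power, SD 8 |
|---|---|---|---|
| 0 | 3.0 | 70.5% | 46.6% |
| 10% | 2.7 | 61.4% | 39.3% |
| 20% | 2.4 | 51.6% | 32.3% |
| 30% | 2.1 | 41.7% | 25.9% |
| 50% | 1.5 | 23.9% | 15.3% |

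The value at f = 0 is below 80% because N was derived from a one-sided non-inferiority formula, whereas the planned test is two-tailed for difference.

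**The case against.** Admitting known diabetics is a legitimate pragmatic choice: the Introduction frames the evidence gap around hospitalized patients with type 2 diabetes. Glucose below 10 at entry need not stay there. The outcome is mean daily glucose over the whole stay, oral drugs are stopped on admission, and the protocol says corticosteroids are often used. The regimens could therefore still differ in these patients. This stands, and it is why the power figures are only an illustration.

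A reader might also infer three stronger things that the documents do not support:

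- **That these entrants are normoglycemic.** The route has no lower glucose limit, but it also admits patients above 7.8 and below 10 mmol/L, who are hyperglycemic by the Introduction's definition.
- **That none of them has a starting dose.** Previously insulin-treated patients with a known dose do.
- **That they push the trial toward a false claim of non-inferiority.** Non-inferiority appears only in the sample-size paragraph; no test or confidence interval is planned against the 3 mmol/L margin. Nor would such a claim be false for the patients enrolled: if their average difference is 2.4 mmol/L, it does lie inside the margin. The issue is which population the answer describes, not an inflated error rate. Dilution would mislead in that direction only if a non-significant difference were read as showing non-inferiority.

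None of this removes the conflict between entry rule, stated population and starting rules, or the two versions of the criteria.

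**Conclusion.** The concern holds as an inconsistency that affects who is randomised, how some are started on insulin, and whose data are kept. That part rests on the text alone.

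The statistical consequence is conditional. A fall in power from 70.5% to 51.6% requires a 20% share, zero difference between regimens in that share, a 3 mmol/L difference in the rest, and SD 6. The documents supply the 3 and the 6, the 3 as a margin rather than an expected difference. They supply neither the share nor the effect, so the true loss could be negligible. An effect on the frequency of hypoglycemia is plausible but cannot be sized from the documents.

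This should be corrected. It does not invalidate the design.

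**What to change.** 1. Reconcile the inclusion criterion, the stated population and objectives, and the starting rules in Study Procedure, so that every eligible patient falls under a stated rule. The clinical threshold and the dose are for the investigators to decide.
2. Use one diabetes-history definition and one glucose threshold in the summary, abstract, Inclusion criteria and Study Procedure.
3. Record entry route (glucose criterion met, or history only) and glucose before randomisation.
4. Keep all randomised patients as the primary analysis set, align the data-discard rule with that, and prespecify a supporting analysis of mean daily glucose and hypoglycemia by entry route.

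Making the glucose-qualified subset primary is not recommended. On the plan's non-inferiority formula with SD 6, power is Φ(3/(6 × √(2/n)) − 1.645), which is about 72% at 40 per arm (a 20% share removed) and about 67% at 35 per arm (30% removed), against the 80% planned.

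The cost is protocol wording, one extra analysis, and possibly a slightly smaller recruitment pool, depending on how the criterion is reconciled. The extra analysis will be imprecise: with a 20% share, the history-only group has 10 per arm, and its 95% interval for the difference is about ±1.96 × 6 × √(2/10) = ±5.3 mmol/L.

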In different countries, basal-bolus therapies with insulin analogs are being used more commonly. But intermediate-acting and regular human insulin are also observed to have almost similar efficacy and safety (12,14). No inpatient trials have been conducted in our region to determine optimal treatment regimens for hospitalized patients with T2DM in special situation like acute stroke. As there are significant differences in patient demographics, admission cause, feeding practice and availability of hospital resources between patients of developed and developing countries, the choice of agents may not be similar (15,16). In this background, the present study aims to compare the efficacy and safety of conventional human insulin (regular insulin and intermediate acting NPH insulin) to newer analog insulin (basal insulin glargine with rapid acting insulin aspart) in acute stroke patients with hyperglycemia admitted in a referral tertiary neuroscience institute of Dhaka.

RATIONALE:

One in five patients hospitalized for acute stroke has hyperglycemia. For optimum outcome of these patients, proper glycemic control is essential. Acute stroke patients, who need hospitalization, are usually unable to take food normally and they are fed through nasogastric tube with small frequent feeding (200 ml, 2-hourly, 10 feed/day). It is not clear which insulin regimen will suit better to these type of feeding practice. Moreover, corticosteroids (dexamethasone) are often used in these patients as treatment adjunct which further challenges glucose homeostasis. Different insulin regimens are used in such patients but none is validated in clinical trials. Episodes of hypoglycemia may cause further neurological deterioration in acute stroke patients. So regimen with less chance of hypoglycemia needs to be identified. Although analog insulins are observed to have less chance of hypoglycemia, they are costly and had not been well studied in our setting. It is essential for us to know the efficacy and safety of analog insulin regimen in comparison to human insulin, so that appropriate management decision can be made

OBJECTIVES:

General objective:

- To compare the efficacy and safety of human insulin (regular insulin and intermediate acting NPH insulin) to analog insulin (basal insulin glargine and rapid acting insulin aspart) in hospitalized acute stroke patients with hyperglycemia

Specific objectives:

In hospitalized acute stroke patients with hyperglycemia -

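### Correction doses in the analog arm are regular human insulin, so the human-versus-analog contrast is blurred and the stated conclusion needs a qualification

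*Combined protocol and SAP*

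**What the plan says.** The correction rule is in the Study Procedure: "Supplemental regular insulin will be given in addition to scheduled mealtime insulin for BG >10 mmol/L using a supplemental insulin protocol". It closes a paragraph whose first sentence sets the glucose target for both groups, and it makes no exception for either arm. The supplemental scale is not reproduced.

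The Introduction states the contrast under study as "conventional human insulin (regular insulin and intermediate acting NPH insulin) to newer analog insulin (basal insulin glargine with rapid acting insulin aspart". The Specific objectives include "To assess the efficacy and safety of insulin analog (basal insulin glargine and rapid acting insulin aspart", and also, at regimen level, "To compare the efficacy and safety of two insulin regimen". In the Study Procedure, regular insulin is the human arm's scheduled bolus and aspart is the analog arm's. Both are given at about 6 am, 12 pm and 6 pm, and each makes up half of the total daily dose in its arm.

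For patients not known to have diabetes, the starting rule is "insulin therapy will be started if admission BG is >10 mmol/L in two or more occasions". The summary's expected outcome reads "The result will clearly show the efficacy and safety of newer insulins in comparison to conventional human insulin".

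**The concern.** Followed as written, the plan gives analog-arm patients the comparator's bolus insulin whenever a premeal reading exceeds 10 mmol/L. This need not be rare. The trigger is the upper end of the target range, BG is checked before all three boluses, and the same cut-off starts treatment in patients without known diabetes.

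The Rationale gives the reason for testing analogs: "Although analog insulins are observed to have less chance of hypoglycemia, they are costly and had not been well studied in our setting". Hypoglycemia is the primary safety outcome under Outcome variables. An event that follows aspart and regular insulin given together cannot be cleanly attributed to the analog regimen.

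A shared product also makes the arms more alike, which could move the result toward no difference. Under Sample Size the protocol says "Sample size was calculated according to following formula for non-inferiority trial", and in a non-inferiority trial a shift of that kind favours the conclusion sought.

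**Working it through.** **Reading the rule against the arm definitions.**

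- Human arm: NPH plus regular insulin, with regular insulin for correction. All of it is human insulin.
- Analog arm: glargine plus aspart, with regular insulin for correction. The Introduction classes regular insulin as human insulin, so the correction comes from the other arm's regimen.
- The basal half of the scheduled dose (glargine against NPH) is not affected.

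**The plan's own figure.** The protocol states no figure for supplements. Its sample size shows only that the trial was sized for non-inferiority: 2 × ((1.645 + 0.845)/3)² × 6² = 49.6, rounded to 50 per group.

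**Scheduled aspart per injection, from the protocol alone.** The starting total daily dose for patients without a known prior insulin dose is 0.3–0.4 U/kg (admission BG 10–15 mmol/L) or 0.5–0.6 U/kg (BG >15). Half is aspart, in three equal doses, so d = rate × 0.5 / 3:

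| Daily rate (U/kg) | d (U/kg) | d at 60 kg (assumed) | Daily total T at 60 kg |
|---|---|---|---|
| 0.3 | 0.050 | 3 U | 18 U |
| 0.4 | 0.067 | 4 U | 24 U |
| 0.5 | 0.083 | 5 U | 30 U |
| 0.6 | 0.100 | 6 U | 36 U |

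A supplement equal to d makes regular insulin half of that injection's bolus units. This needs no assumption about the scale.

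**Illustrative shares.** The supplement s is assumed to be 2–4 U for BG 10–15 and 4–6 U for BG >15.

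- Share of bolus units at a supplemented injection, s/(s + d):
  - BG 10–15: 2/(2 + 4) = 33% to 4/(4 + 3) = 57%.
  - BG >15: 4/(4 + 6) = 40% to 6/(6 + 5) = 55%.
- Share of the day's insulin with one supplement, s/(s + T):
  - BG 10–15: 2/(2 + 24) = 8% to 4/(4 + 18) = 18%.
  - BG >15: 4/(4 + 36) = 10% to 6/(6 + 30) = 17%.

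**Sensitivity to weight, 50–70 kg, same supplements.**

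- Injection share:
  - BG 10–15: 2/(2 + 4.67) = 30% to 4/(4 + 2.5) = 62%.
  - BG >15: 4/(4 + 7) = 36% to 6/(6 + 4.17) = 59%.
- Day share:
  - BG 10–15: 2/(2 + 28) = 7% to 4/(4 + 15) = 21%.
  - BG >15: 4/(4 + 42) = 9% to 6/(6 + 25) = 19%.

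These are shares at starting doses on a day with one supplement. The number of such days is unknown, and no effect on mean BG, hypoglycemia or error rates follows from these figures.

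**The case against.** The strongest reply is that this is an openly stated correction rule applied equally to both randomized groups. Much of the protocol asks a regimen-level question, and for regimens with a common correction the comparison is valid. That stands. The protocol does not describe its comparison that way, however, and the expected conclusion carries no such limit.

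A second reply is that the Introduction calls thrice-daily regular insulin simple and suited to the feeding practice, and describes analogs as costly and of limited availability. The feeding remark describes existing local practice. It does not justify regular-insulin correction in an arm that already receives aspart at the same three times. Supply is a real constraint, and the fallback below allows for it.

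Third, any correction, together with daily titration to a shared target, pulls mean BG together whichever product is used. That is true, and matched corrections would not remove it. They would remove only the shared product, whose separate effect cannot be sized.

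Fourth, only the sample-size formula is non-inferiority. The Statistical analysis section plans two-tailed difference tests, under which dilution would make an analog advantage harder to show. This limits the non-inferiority argument, but the possible shift is still toward no difference.

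Finally, the shares rest on an assumed scale and weight. The threshold for starting insulin does not show how often treated patients exceed 10 mmol/L, and patients with treated diabetes can enter without a reading of 10 or more. In the 60 kg illustration, at least 82% of the day's insulin remains analog with one supplement. All of this stands, and it is why no dilution effect is claimed.

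**Conclusion.** The concern holds. As written, the analog arm receives human bolus insulin for every correction, while the objectives and the expected conclusion describe a contrast without that overlap. The randomization is not undermined. What suffers is the interpretation, mainly the attribution of hypoglycemia to the analog regimen.

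From the protocol alone, a supplement of 0.05–0.10 U/kg, equal to the scheduled starting aspart dose, makes half of that injection's bolus regular insulin. The percentage ranges depend on the assumed weights and supplement sizes. This is a worthwhile, inexpensive improvement with an effect that cannot be quantified. Confidence is moderate because supplement frequency is unknown.

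**What to change.** Change the correction sentence in the Study Procedure so that supplements are given as each arm's own bolus insulin: regular in the human arm, aspart in the analog arm. Use the same BG trigger and unit scale in both. The arms would still differ in schedule (NPH twice daily, glargine once daily), so the result would be a comparison of human and analog regimens, without human insulin in analog-arm corrections.

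The cost is one sentence and some extra aspart in 50 patients, with no added visits or measurements. At 60 kg with the assumed supplements, one supplement adds, relative to that day's scheduled aspart (s/3d), 2/12 = 17% to 4/9 = 44% for BG 10–15, and 4/18 = 22% to 6/15 = 40% for BG >15. The documents give no insulin price, and the budget has no insulin line.

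If supply rules this out, keep regular insulin for both arms. Word the objectives and expected conclusion as a comparison of scheduled basal-bolus regimens with common regular-insulin correction, and report supplemental units per patient-day by arm beside mean BG and hypoglycemia. Total daily dose is already a secondary outcome but is not split into scheduled and supplemental units. This fallback costs one sentence and one extra summary. It is the weaker option because it describes the overlap without removing it.

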Except anti-diabetic treatment, other treatments will be continued as per the decisions of the treating physicians. If NG feeding is discontinued and patient is kept NPO, conventional group will receive neutralizing insulin with any dextrose containing fluid along with low dose NPH insulin, if needed. Modern insulin group will receive neutralizing insulin with any dextrose containing fluid with glargine insulin as before.

After recruitment, each recruited patient will be visited daily (even in holidays according to a predefined schedule) by one of the investigators and insulin dose will be adjusted according to glucose profile of previous day. Insulin injection and capillary blood glucose monitoring by glucometer will be done by trained nurses as part of their routine patient care. Doctors and nurses on duty will be provided with cell number of the investigators who will receive call on 24/7 basis for any emergency or uncertainty regarding management of hyperglycemia.

Hypoglycemia is regarded as the only short-term adverse event of insulin. As both treatment arms will use established and recognized insulin regimen, no compensation will be provided to the patient or his/her attendants in case of any adverse event. As most of the hospitalized patients have severe stroke with case fatality rate around 20%, death will not be regarded as parameter of primary treatment outcome.

During discharge, last in-hospital insulin dose will be continued with education to the caregiver regarding insulin injection and glucose monitoring technique. No follow up visit is included in the study.

Protocol deviation and protocol violation:

Deviation to protocol will be recorded and reported to ethical committee as soon as possible. Failure to obtain informed written consent, use of incorrect insulin regimen, not fulfilling inclusion and exclusion criteria will be regarded as protocol violation and will be reported to ethical committee immediately. In case of protocol violation, the data of related participant will be discarded.

Outcome variables

The primary efficacy outcome of the study will be the differences in glycemetic control between groups, as measured by mean daily BG concentration during the hospital stay.

The primary safety outcome will be the frequency of hypoglycemic events (BG <3.9 mmol/L).

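### Corticosteroid use, which the protocol calls common and glucose-raising, has no stated place in randomisation, analysis or between-arm reporting: a modest loss of precision and a missing check, not a demonstrated bias

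*Combined protocol and SAP*

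**What the plan says.** The Introduction (Section-C) states that "many acute stroke patients receive corticosteroid therapy, which further deteriorates glycemic status". The Rationale adds that "corticosteroids (dexamethasone) are often used in these patients as treatment adjunct which further challenges glucose homeostasis". Neither gives a rate of use or a size of effect.

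Steroids are not mentioned after the Rationale. Their use is not an exclusion criterion. Study Procedure deals with all background care in one sentence: "Except anti-diabetic treatment, other treatments will be continued as per the decisions of the treating physicians". The Methodology section describes the design as "Type of study: Single-center, open-label, randomized trial". Allocation is made "following a computer-generated randomization table", with no stratification or minimisation factor stated, to 50 patients per arm.

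Under Outcome variables, the primary efficacy outcome is the difference between arms in glycaemic control, "as measured by mean daily BG concentration during the hospital stay". Statistical analysis gives a t-test or Mann-Whitney test for continuous variables, with no covariate, subgroup or sensitivity analysis. One specific objective is to describe the socio-demographic and clinical characteristics of the two arms. It does not name steroids.

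**The concern.** The plan identifies a common treatment that acts directly on the primary outcome and then makes no stated use of that knowledge. Two things are at stake.

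The first is precision. If steroid use explains part of the variation in mean daily BG, an unadjusted comparison carries that variation as noise. In a single trial of 50 per arm, an uneven split also moves the estimate, and readers cannot judge by how much unless steroid use is tabulated by arm.

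The second is interpretation. The two regimens have visibly different schedules and the trial is open-label, so the physicians who decide on steroids can probably see both the arm and the daily glucose. If steroid use came to differ by arm for that reason, the comparison would no longer be of insulin regimens alone. Nothing in the written analysis would show this.

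Admission BG or HbA1c cannot stand in for steroid status, because neither reflects a course started at or after admission.

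**Working it through.** **Inputs from the documents** (Sample Size): 50 per arm, margin 3 mmol/L, one-sided α 0.05 (z = 1.645), power 80% (z = 0.845). The SD is labelled 8, but 6 is put into the formula.

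**Assumed inputs**, because the documents give none: steroid use p of 20-50% and a steroid effect g of 2-4 mmol/L on mean daily BG.

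**1. The plan's own figure.** 2 × ((1.645 + 0.845)/3)² × 6² = 49.6, which rounds up to 50 per arm. It is reproduced with SD 6, so SD 6 is used below. The standard error (SE) of the arm difference is 6 × √(2/50) = 1.2 mmol/L.

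**2. Size of chance imbalance.** The SD of the difference in steroid proportion is √(2p(1−p)/50).

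| p | SD of difference | × 1.96 | P(imbalance ≥ 10 points) | P(imbalance ≥ 20 points) |
|---|---|---|---|---|
| 0.2 | 0.080 | 0.157 | 0.26 | 0.02 |
| 0.3 | 0.092 | 0.180 | 0.33 | 0.04 |
| 0.5 | 0.100 | 0.196 | 0.37 | 0.06 |

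The probabilities are from the exact binomial distribution.

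**3. Effect on the realised estimate.** Shift = g × imbalance. At the 95% limit this runs from 2 × 0.157 = 0.31 to 4 × 0.196 = 0.78 mmol/L. That is 10-26% of the 3 mmol/L margin and 0.31/1.2 = 0.26 to 0.78/1.2 = 0.65 of one SE. A more typical case is a one-SD imbalance at p = 0.3 and g = 3: 0.092 × 3 = 0.28 mmol/L, or 0.23 SE.

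**4. Does chance imbalance distort the test?** No. Steroid-related variation is part of the outcome SD and so of the SE. In 40,000 simulated trials per setting (p = 0.3 or 0.5, g = 2 or 4, total SD 6), the two-sided 5% t-test rejected in 4.9-5.0% of trials with no insulin effect.

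**5. Precision lost by leaving the factor out.** Share of variance explained = g²p(1−p)/SD²; the SE is multiplied by √(1 − share).

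| p | g | Share | SE multiplier | SE (mmol/L) |
|---|---|---|---|---|
| 0.3 | 2 | 0.84/36 = 2.3% | 0.988 | 1.19 |
| 0.5 | 2 | 1.00/36 = 2.8% | 0.986 | 1.18 |
| 0.3 | 4 | 3.36/36 = 9.3% | 0.952 | 1.14 |
| 0.5 | 4 | 4.00/36 = 11.1% | 0.943 | 1.13 |

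The SE falls by about 1-6%. With the labelled SD of 8 the gain would be smaller: shares of 0.84/64 = 1.3% to 4/64 = 6.3%, or about 1-3% of the SE.

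**6. If steroid use differed by arm systematically.** Bias = g × difference in use. This is hypothetical. The rates are normal approximations at SE 1.2.

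| Bias (mmol/L) | Example | Two-sided 5% false positives | False non-inferiority (one-sided 5%, true difference 3) |
|---|---|---|---|
| 0.2 | 10 points × 2 | 5.3% | 7.0% |
| 0.4 | 20 points × 2 | 6.3% | 9.5% |
| 0.8 | 20 points × 4 | 10.2% | 16.4% |

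**The case against.** A reader might infer that steroid imbalance can pass as an insulin effect, and so that the primary comparison is biased. The documents do not support that reading. Randomisation balances steroid use in expectation, and step 4 shows that the test keeps its error rate. The same could be said of any unstratified prognostic factor, and simple randomisation with an unadjusted test is valid. This part of the case against the point stands in full.

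A reader might also infer that unblinded physicians will prescribe steroids differently by arm. The documents permit this but do not show it. Both arms receive active insulin to one glucose target, and investigators, not the treating physicians, adjust the insulin dose. Stratifying on status at randomisation would not prevent such differences anyway.

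A third tempting claim is that imbalance could not be detected. That is unproven. The predesigned questionnaire is not in the supplied text and may record steroids, and one objective covers clinical characteristics by arm. What can be shown is that the written analysis names no such comparison.

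The size is also open to challenge. The 0.78 mmol/L figure combines the highest assumed use, the largest assumed effect and a 95%-limit imbalance, and is still below one SE at SD 6. Daily titration of both arms to the same target should absorb part of the steroid effect. It would do so only in part, since doses rise by 10-20% a day while the outcome averages the whole stay. What is absorbed would move into total daily insulin dose, a secondary outcome.

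What survives is narrower. The protocol itself names the prognostic factor, using it costs little, and the plan states no use of it and no between-arm check.

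**Conclusion.** The point holds as a modest weakness of design and reporting, not as a demonstrated bias. Omitting steroid status at randomisation costs about 1-6% of the SE (1.20 falling to about 1.13-1.19 mmol/L with adjustment). This assumes 30-50% use at randomisation, a 2-4 mmol/L effect that persists despite titration, and SD 6. Chance imbalance can shift the single estimate by roughly 0.3-0.65 of an SE at its 95% limits without affecting the validity of the test. Only arm-dependent steroid use after randomisation could produce real bias. The documents leave that possible, give no evidence for it, and state no means of looking for it. Because rate and effect are assumed, these sizes are illustrations and not estimates.

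**What to change.** 1. Record at randomisation whether a corticosteroid is being given or has been ordered (yes/no). Split the computer-generated table into two lists on that factor, each in permuted blocks.
2. Replace the unadjusted test of mean daily BG with a prespecified linear model containing treatment arm and steroid status at randomisation. Report the adjusted difference with its confidence interval. A factor used to stratify should be in the model, or its precision gain is not credited.
3. Add daily corticosteroid use and dose to the questionnaire, and report steroid-days by arm descriptively. Do not use them as a covariate: use after randomisation may follow from allocation, and adjusting for it could itself introduce bias.

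Items 1 and 2 give the precision gain. Item 3 is the only one that addresses differential use, and it can reveal it but not correct it. Physicians' prescribing is unchanged, and the sample size stays at 50 per arm. The cost is two allocation lists instead of one, one questionnaire line per day, one model term and slightly more work at allocation.
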